8.1.3 DEFINITION OF UNANTICIPATED PROBLEMS (UP)

An AE observed during the conduct of a study should be considered an Unanticipated Problem (UP) involving risk to human subjects, and be reported to the IRB, only if it was unexpected, serious, and would have implications for the conduct of the study (e.g., requiring a significant, and usually safety-related, change in the protocol, such as revising inclusion/exclusion criteria or including a new monitoring requirement, informed consent, or IB). The occurrence of such an event would suggest that the research places study participants or others at a greater risk of harm.

FDA recommends that there be careful consideration of whether an AE is a UP that must be reported to IRBs. In summary, FDA believes that only the following AEs should be considered as UPs that must be reported to the IRB:

- A single occurrence of a serious, unexpected event that is uncommon and strongly associated with drug exposure (such as angioedema, agranulocytosis, hepatic injury, or Stevens-Johnson syndrome)
- A single occurrence, or more often a small number of occurrences, of a serious, unexpected event that is not commonly associated with drug exposure, but uncommon in the study population (e.g., tendon rupture, progressive multifocal leukoencephalopathy)
- An AE that is described or addressed in the IB, protocol, or informed consent documents, but occurs at a specificity or severity that is inconsistent with prior observations
- An SAE that is described or addressed in the IB, protocol, or informed consent documents, but for which the rate of occurrence in the study represents a clinically significant increase in the expected rate of occurrence (ordinarily, reporting would only be triggered if there were a credible baseline rate for comparison)
- Any other AE or safety finding (e.g., based on animal or epidemiologic data) that would cause the sponsor to modify the IB, study protocol, or informed consent documents, or would prompt other action by the IRB to ensure the protection of human subjects

8.2 CLASSIFICATION OF AN ADVERSE EVENT

8.2.1 SEVERITY OF EVENT

The Investigator will assess AEs for severity utilizing the CDISC AESEV, which classifies AEs as mild, moderate, or severe ([Table 1](#)).

Table 1: CDISC Definitions of Adverse Event Severity

CDISC Submission Value	CDISC Definition
MILD	A type of adverse event that is usually transient and may require only minimal treatment or therapeutic intervention. The event does not generally interfere with usual activities of daily living.
MODERATE	A type of adverse event that is usually alleviated with additional specific therapeutic intervention. The event interferes with usual activities of daily living, causing discomfort but poses no significant or permanent risk of harm to the research participant.
SEVERE	A type of adverse event that interrupts usual activities of daily living, or significantly affects clinical status, or may require intensive therapeutic intervention.

8.2.2 RELATIONSHIP TO STUDY AGENT

The relationship of the study treatment to an AE will be determined by the Investigator based on the following definitions:

1. Not Related

The AE is not related if (1) exposure to the study medication or administration of the study injection has not occurred **or** (2) the occurrence of the AE is not reasonably related in time **or** (3) the AE is considered related to another event, medical condition, or product not associated with the study medication or the study injection.

2. Unlikely Related

The AE is unlikely related if (1) the AE is unlikely related in time **or** (2) the AE is considered unlikely to be related to use of the study medication or study injection (i.e., there are no facts [evidence] or arguments to suggest a causal relationship), or the AE is considered possibly related to another event, medical condition, or product not associated with the study medication.

3. Possibly Related

The AE is possibly related if (1) the study medication or the study injection and AE are considered reasonably related in time **and** (2) the AE could equally be explained by causes other than exposure to the study medication or the study injection.

4. Probably Related

Exposure to study medication or administration of the study injection and AE are probably related if (1) the study medication or study injection and AE are considered reasonably related in time **and** (2) the study medication or study injection is more likely than other causes to be responsible for the AE **or** is the most likely cause of the AE.

8.2.3 EXPECTEDNESS

The Sponsor will be responsible for determining whether an AE/SAE is expected or unexpected. An AE/SAE will be considered unexpected if the nature, severity, or frequency of the event is

not consistent with the risk information previously described for the study agent in the IB or is not listed in the IB at the specificity or severity that has been observed.

8.3 TIME PERIOD AND FREQUENCY FOR EVENT ASSESSMENT AND FOLLOW-UP

The reporting period for AEs starts after the injection of study medication on Day 1 and ends after the final study visit.

AEs that are ongoing at a subject's last visit will be followed for 30 days after administration of the last dose of study medication or until resolution, whichever comes first. Resolution is defined as the return to baseline status or stabilization of the condition. SAEs that are ongoing at a subject's last visit will be followed until resolution.

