Subjects who complete Phase A will be eligible to enter the extension phase, Phase B, for an additional 52 weeks of treatment. Subjects will remain on their randomized treatment (SM04690 or placebo) for the additional year. Each subject that consents to enter Phase B will receive an injection at Week 52 (EOSa) and Week 76 with follow-up clinic visits scheduled at Weeks 64, 76, 88, and 104 (EOSb) or ET. Specific timing of protocol procedures is described in the Schedule of Events Table ([Section 7.3.7](#)). Specific timing of electronic diary and questionnaire

completion is described in the Schedule of Electronic Diary and Questionnaire Completion Table (Section 7.3.8).

Primary analysis of Phase A data will be completed after the last subject completes Week 52 (EOSa). While the Sponsor will be unblinded to study treatment after the Phase A analysis (after the last subject completes Week 52 [EOSa]), the Investigator and the subject will remain blinded.

In Phase B, qCT will be performed at Weeks 64, 76, 88, and 104 (EOSb) or ET. DXA will be performed at Weeks 76 and 104 (EOSb) or ET. Bone and cartilage biomarkers will be assessed at Weeks 64, 76, 88, and 104 (EOSb) or ET. Radiographic images of the knees will be performed at Weeks 76 and 104 (EOSb) or ET.

Subjects will be required to complete the following:

- Daily pain NRS
- Monthly completion of the WOMAC
- Monthly completion of Patient Global Assessment

Recording of signs and symptoms of study medication intolerance and AE reporting will start following the first injection of the study medication and continue until the subjects complete their last study visit. All AEs, whether volunteered, elicited, or noted during examination, will be recorded throughout the study.

Subject Re-Screening

Subjects are allowed to be re-screened once. Re-screens are limited to subjects who did not meet inclusion/exclusion criteria due to a transient reason. Transient refers to self-limiting and predictably resolving conditions or acute events (e.g., common cold or otitis media), reversible medical conditions that are successfully treated (e.g., anemia successfully treated by infusion), and/or being unable to comply with study procedures due to administrative convenience (e.g., family issues or attending to a private matter). Diary non-compliance is not a transient event and subjects with diary non-compliance may not be re-screened.

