5.3 LIFESTYLE GUIDELINES

5.3.1 CONTRACEPTION

From Screening Visit 1 until their last study visit, all subjects must agree to be strictly abstinent from sexual intercourse or use an acceptable form of contraception as defined by this protocol if the subject or their partner is capable of becoming pregnant.

Acceptable forms of contraception are:

1. Use of a condom for males with a vasectomy (vasectomy must have been performed at least 6 months prior to Screening Visit 1)
2. Males without a vasectomy or a vasectomy performed within 6 months prior to Screening Visit 1 must use a condom and be instructed that their female partner(s), if any, must be

post-menopausal or permanently surgically sterile, or must use another form of birth control which includes the following:

- a. Barrier methods of contraception such as a diaphragms or cervical/vault caps
- b. Established hormonal contraceptive methods. Females who are using hormonal contraceptives must have had consistent use of the same hormonal contraceptive product for at least 4 weeks prior to dosing and must continue to use the same contraceptive during the study
- c. Intrauterine device (IUD)
- d. Tubal ligation/occlusion/division

3. Women who are not post-menopausal or permanently surgically sterile must agree to use birth control (as described in #2 above) and be instructed that their male partner(s) must use a condom

Subjects who withdraw from the study after receiving study medication should remain on an acceptable form of contraception for 24 weeks after their last study injection.

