5.5.2 HANDLING OF PARTICIPANT WITHDRAWALS OR TERMINATION

In case of premature discontinuation of study participation, ET procedures should be conducted within 14 days of discontinuation for any subject who discontinues after the Day 1 visit, if possible. The date the subject is withdrawn from the study and the reason for the discontinuation should be recorded on the eCRF. The Investigator or designee must complete all applicable eCRF pages for subjects who discontinue from the study prematurely.

Replacement of subjects who withdraw or discontinue prematurely is not allowed.

Subjects who are withdrawn from study medication for safety reasons will continue with all planned study visits per protocol, without any further dosing.

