7. STUDY PROCEDURES AND SCHEDULE

7.1 STUDY PROCEDURES/EVALUATIONS

7.1.1 STUDY SPECIFIC PROCEDURES

Collection of Adverse Events Data

Data regarding AEs will be collected in this study. AEs are events that occur during the course of the study that are not present prior to Day 1 study medication injection, or, if present at the time of study medication injection, have worsened in severity during the course of the study. AEs will be assessed at each study visit from the time of study medication injection on study visit Day 1 through the subject's last study visit.

Each subject will be observed and queried by the Investigator or the Investigator's designee at each study visit for any continuing AEs or new AEs since the previous visit. The subject may be asked to return to the site for an unscheduled visit if an AE occurs between study visits, and if, in the opinion of the Investigator, the AE requires a study visit for full evaluation. Any AE reported by the subject or noted by the Investigator or the Investigator's designee will be recorded within the eCRF. The following information will be recorded for each AE: description of the event, date of onset and resolution, etiology, and severity as assessed by the Investigator according to the Clinical Data Interchange Standards Consortium (CDISC) Severity/Intensity Scale for Adverse Events (AESEV) ([Table 1](#)), causal relationship to study medication, outcome, and any treatment given.

In this protocol, signs and symptoms of exacerbation or worsening of target knee OA will be captured in the context of efficacy assessments and recorded on specific pages of the eCRF.

Anticipated fluctuations or anticipated deterioration (in the opinion of the Investigator) of the underlying disease (target knee OA) will not be considered as AEs nor captured on the AE page of the eCRF.

Whenever possible, it is preferable to record a diagnosis as the AE term rather than a series of symptoms relating to a diagnosis. Fluctuations of pre-existing conditions, including the disease under study, that do not represent a clinically significant exacerbation or worsening, need not be considered AEs.

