^b At Day 1, all procedures should be performed prior to study medication injection except for collection of AE and concomitant procedures/medication data.

^c At Week 24, 52 (EOSa), and 76, all procedures should be performed prior to study medication injection.

^d Review medical history to capture End Date(s), if applicable, of any ongoing medical history(ies) collected at screening.

^e Urine pregnancy test on Day 1 will only be performed on female subjects of childbearing potential.

^f Concentrations of bone and cartilage biomarkers are analyzed in the serum.

^g Electronic diary devices will be provided to subjects at Screening Visit 2; subject electronic diary and questionnaire training will be conducted at Screening Visit 2.

^h Electronic diary compliance for daily pain NRS over the screening period will be reviewed at Day 1 prior to randomization to determine subject eligibility.

ⁱ WOMAC questionnaire will be reviewed at Day 1 prior to randomization to determine subject eligibility.

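### AE reporting closes at the last study visit with no minimum time after the last injection, so new events are poorly captured in a subject who leaves the study soon after a dose

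*Protocol*

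**What the plan says.** Three places in the Protocol set the end of AE collection, and they agree.

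- Section 8.3: "The reporting period for AEs starts after the injection of study medication on Day 1 and ends after the final study visit".
- Section 4.1: recording is to "continue until the subjects complete their last study visit".
- Section 7.1.1: AEs are assessed "from the time of study medication injection on study visit Day 1 through the subject's last study visit".

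After that visit, Section 8.3 covers only events that have already begun. For non-serious events: "AEs that are ongoing at a subject's last visit will be followed for 30 days after administration of the last dose of study medication", or to resolution if that is sooner. For serious events: "SAEs that are ongoing at a subject's last visit will be followed until resolution".

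Section 5.5.1 lets subjects leave at any time. For those who do, Section 5.5.2 says that "ET procedures should be conducted within 14 days of discontinuation for any subject who discontinues after the Day 1 visit, if possible". The clock starts at discontinuation, not at the last injection. On the order of procedures at the later injection visits, footnote c of the Section 7.3.7 schedule says: "At Week 24, 52 (EOSa), and 76, all procedures should be performed prior to study medication injection".

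Section 8.4.2 requires SAEs to be reported within 24 hours of notification. It gives no end date and refers to a study manual that is not among the documents.

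**The concern.** Safety and tolerability are the primary objective, and AE tables carry much of that assessment. The close of the reporting period depends on when the subject is last seen and not on when the subject was last dosed. For a subject who stays, this does no harm. For one who leaves the study shortly after an injection, the period after that dose may be cut to a few days or to nothing.

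The analysis does not adjust for this. SAP Sections 7.6 and 7.7 place every subject with at least one injection (or at least one Phase B injection) in the safety set, and SAP Section 10.1 reports the number and percent of subjects with each event. A subject who leaves just after the Week 52 injection therefore counts fully in the Phase B denominator with almost no Phase B observation, and appears event-free for that phase.

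**Working it through.** The Protocol states no figure for this point, so the check is a reading of the text plus calendar arithmetic.

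**1. Completers.** Injections are planned on Days 1, 169, 365 and 533, and final visits on Day 365 (Phase A) or Day 729 (Phase B).

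- Last injection to final visit: 365 − 169 = 196 days, and 729 − 533 = 196 days.
- With visit windows (taking ±3 days at Week 24, as in Section 7.3.3) and the permitted two-week injection delay, the shortest gap is 729 − (533 + 7 + 14) = 175 days. The longest is (365 + 7) − (169 − 3) = 206 days.

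Completers have ample observation. For them the 30-day rule for ongoing AEs has expired 196 − 30 = 166 days before the final visit. The rule can operate only when the last visit falls within 30 days of a dose, which is the group at issue here.

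**2. A subject who leaves on the day of an injection.** If the ET visit comes *x* days later, reporting closes on post-dose day *x*, and 30 − *x* days of the Protocol's own 30-day interval are closed to new events.

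| ET visit, days after injection | Days of 30 closed |
|---|---|
| 0 | 30 |
| 1 | 29 |
| 7 | 23 |
| 14 | 16 |

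**3. No ET visit.** After the Week 24, 52 and 76 injections, the next scheduled visits are Weeks 36, 64 and 88, each 84 days later (253 − 169, 449 − 365, 617 − 533). For an early leaver the injection visit is then the last visit, and by footnote c its procedures precede the injection. No AE query after that dose is planned. Day 1 differs: footnote b and Section 7.3.2 place AE collection after the injection.

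**4. How many subjects.** The documents give no dropout rate. Assume 10, 20 or 30 of 100 subjects leave, evenly over the 729 days.

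- Days within 30 days of an injection: 4 × 30 = 120, and 120/729 = 16.5%.
- Leavers inside such a window: 10, 20 or 30 × 0.165 = 1.6, 3.3 or 4.9, both arms together.

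**5. Days lost per such leaver.** Take the leaving day as uniform on 0 to 30.

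- Events captured up to the day of leaving and no later: 30/2 = 15.0 days on average.
- ET visit uniform over the next 14 days: (30³ − 16³)/(3 × 14 × 60) = 22,904/2,520 = 9.1 days.

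**6. From leavers to missed cases.** A leaver is a missed case only if a new AE starts in the lost days. If that chance is 10 to 30% (assumed), the total is 1.6 × 0.10 ≈ 0.2 to 4.9 × 0.30 ≈ 1.5 subjects. With 50 per arm, one subject is 1/50 = 2 percentage points for a given event, provided the same event was not already recorded for that subject.

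**The case against.** Several points on the other side stand.

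- **SAEs.** A reader might infer that a new SAE after an early last visit is not reportable. The text does not say so. The sentence that closes reporting names AEs only, and Section 8.4.2 asks for all SAEs on notification with no end date. What is missing is any requirement to elicit a late SAE.
- **Day 1.** A reader might infer that every injection can go without a post-dose query. Because AE collection on Day 1 follows the injection, this applies only to the three later injections.
- **Informative loss.** It is tempting to argue that those who leave after an injection are those who reacted to it, so that the missing events are selective. A reaction that prompts leaving normally begins before the subject leaves, and so inside the reporting period. Section 5.5.2 also has the reason for leaving recorded. What can be lost is a further, later event. Selective loss is plausible but not documented.
- **Safeguards.** Subjects taken off medication for safety (Section 5.5.2) or judged unsuitable for injection (Section 6.1.9) keep all planned visits, and Section 5.5.1 promises best efforts to retain those withdrawn from treatment. These provisions reduce the number affected but do not reach a subject who leaves the study.
- **The comparison intervals.** Section 5.3.1 says that leavers "should remain on an acceptable form of contraception for 24 weeks after their last study injection". That concerns pregnancy and does not define an AE window. The 30-day figure was written for ongoing events, and applying it to new ones is a choice, though a natural one.

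There is also no contradiction to repair, since the three sections agree. The difficulty is a gap they share.

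**Conclusion.** The gap is real and modest. For a subject who leaves the study, not merely study medication, soon after an injection, reporting of new-onset AEs can close 0 to 14 days after the dose. With no ET visit after the Week 24, 52 or 76 injection, there is essentially no planned post-dose AE query. No other provision closes this gap.

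The estimate of about 2 to 5 people rests on an assumed 10 to 30% leaving evenly over time; it would be higher if leaving clusters after injections. A reader might take it as a count of missed events. It counts leavers across both arms, and the number of missed cases would be smaller. The documents do not establish that the AE or SAE tables are materially biased. This is a cheap improvement to ascertainment for the primary objective and not a flaw that undermines the safety analysis.

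**What to change.** In Protocol Section 8.3, and in the matching sentences of Sections 4.1 and 7.1.1, state that the reporting period for new AEs and SAEs ends at the later of the final study visit and 30 days after the last injection. For subjects who leave sooner, obtain the information by one telephone contact at day 30. Naming SAEs explicitly also supplies the end date that Section 8.4.2 lacks. The 30 days is the figure Section 8.3 already uses for ongoing events.

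The cost is a change of wording and one call for a handful of subjects. The limitation is that subjects who withdraw consent fully or are lost to follow-up cannot be reached, so the gap narrows but does not close.

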8.4 REPORTING PROCEDURES

8.4.1 ADVERSE EVENT REPORTING

The Investigator is responsible for reporting AEs to the Sponsor and IRB according to the protocol as well as 21 Code of Federal Regulations (CFR) part 50, part 56, and part 312. The Investigator is responsible for ensuring accurate AE information is reviewed and recorded in the subject source and the AE eCRF in a timely manner. The Sponsor is responsible for submitting reports of AEs associated with the use of study medication that are both serious and unexpected to the FDA according to 21 CFR 312.32. All Investigators participating in ongoing studies with the study medication will receive copies of these reports from the Sponsor for prompt submission to their IRB/EC according to their institution's requirements.

8.4.2 SERIOUS ADVERSE EVENT REPORTING

The Investigator is responsible for reporting SAEs to the Sponsor and IRB according to 21 CFR part 50, part 56, and part 312.

All SAEs must be reported as described in the study manual by the Investigator, Study Coordinator, other designated study personnel, or Clinical Research Associate within 24 hours of notification of the SAE. The Investigator should review the SAE information and sign the SAE report, and the Investigator or designee should submit the SAE report to the Samumed Study SAE email address: [contact] or [contact]. Follow-up information must be detailed in a follow-up SAE report and reported to the Samumed Study SAE email address or fax number as it becomes available. The Investigator also must report all SAEs promptly to the appropriate IRB/EC as required by the institution. Sponsor contact information for questions regarding SAE reporting is provided in [Table 2](#).

Table 2: Sponsor Contact Information for Questions on SAE Reporting

Primary Contact	Alternative Contact
Medical Monitor: [name]	Sr. Manager, Drug Safety and Pharmacovigilance: [name]
Office [contact]	Office [contact]
Cellular: [contact]	Cellular: [contact]
Email: [contact]	Email: [contact]

8.4.3 UNANTICIPATED PROBLEM REPORTING

Incidents or events that meet the criteria for UP (see [Section 8.1.3](#)) require the creation and completion of an UP report. It is the site Investigator's responsibility to report UPs to their IRB and to the Sponsor. The UP report will include the following information:

- Protocol identifying information: protocol title and number, Investigator's name, and the IRB project number;
- A detailed description of the event, incident, experience, or outcome; and
- An explanation of the basis for determining that the event, incident, experience, or outcome represents an UP.

To satisfy the requirement for prompt reporting, UPs will be reported using the following timeline:

- UPs that are SAEs will be reported to the Sponsor and the IRB within 24 hours of the Investigator becoming aware of the event on the SAE report form.
- Any other UP will be reported to the IRB and to the Sponsor within the IRB-required reporting timeframe.

